## 5.2 Handling of Study Interventions

Both the MBRT and SME interventions will follow a session-by-session protocol. They will both be delivered in 8 weekly sessions with a total training time of 17 hours. Both groups include psychoeducation, gentle movement exercises, and weekly homework assignments.

## 5.3 Concomitant Interventions

### 5.3.1 Allowed Interventions

Any prescribed medications are allowed during the course of the study.

### 5.3.2 Required Interventions

There are no required additional interventions.

### 5.3.3 Prohibited Interventions

There are no prohibited interventions in this study.

## 5.4 Adherence Assessment

Participant adherence to intervention will be measured by attendance (completer  $\geq$  6 out of 8 sessions), and 50% completion of assigned audio recorded home practice, tracked using Ilumivu software.

# 6. STUDY PROCEDURES

## 6.1 Schedule of Evaluations

Assessmen	Phone Screen	Baseline, Enrollment, Randomizat ion: Visit 1	Post-interventi on: Visit 2	3 Month Follow-Up: Visit 3	6 Month Follow-Up: Visit 4
Verbal Consent	X				
Inclusion/Exclusion Criteria	X				
Informed Consent	X				
Alcohol Misuse	X	X	X	X	X
Depression	X	X	X	X	X
Suicidal Ideation	X	X	X	X	X
Trauma Symptoms	X	X	X	X	X
Medication Use		X	X	X	X

Assessment	Phone Screen	Baseline, Enrollment, Randomization: Visit 1	Post-intervention: Visit 2	3 Month Follow-Up: Visit 3	6 Month Follow-Up: Visit 4
Current Psychological Treatment		X	X	X	X
Tobacco Use		X	X	X	X
Adverse Childhood Experiences		X			
C-reactive protein		X	X	X	
IL-6		X	X	X	
IL-10		X	X	X	
TNF- $\alpha$		X	X	X	
Aggression		X	X	X	X
Psychological Resilience		X	X	X	X
Sleep Disturbance		X	X	X	X
Mindfulness		X	X	X	X
Self-Compassion		X	X	X	X
Burnout		X	X	X	X
Sustained Attention to Response Task		X	X	X	X
Interoceptive Awareness		X	X	X	X
Perceived Stress		X	X	X	X
Treatment Expectancy/Credibility (MBRT and SME)		X			
Global Impression of Change (MBRT and SME)			X		
Acceptability (procedures)			X		
Acceptability (MBRT and SME)			X		
Compliance (MBRT and SME)			X		

## 6.2 Description of Evaluations

## 6.2.1 Screening Evaluation

### Consenting Procedure

Informed consent will be attained prior to screening and study enrollment (telephone administered by Research Assistant or Project Coordinator). Study staff administering consent will have minimum bachelors level education, and will have completed the human subjects protection trainings. They will be trained and supervised by Drs. [name], [name], or [name]. Interested individuals will call PU (PPB or MPD) or UNM (APD) research offices and be given information about the study. If interested, they will provide consent via REDCap, then complete a phone eligibility screen (see below).

The consent form will include information about randomization, release of information (including data from PPB and APD databases), researchers' responsibilities regarding records collected, DHHS certificate of confidentiality, registration with clinicaltrials.gov, and permission to audio and video record sessions. The signing of this form indicates the study enrollment date.

All signed informed consent forms will be stored in REDCap and printed and stored in a locking file cabinet within study coordinator [name]'s locked research office (PU) or Co-I [name]'s (UNM) locked research lab. Members of the research team will complete a form documenting the informed consent process, which will be stored electronically on the secure REDCap system.

### Screening Procedure

Prior to beginning the phone eligibility screen, administered by a Research Assistant or the Project Coordinator, participants will be informed of the study purpose, procedures, and the randomization process and eligibility criteria. They will provide verbal consent for a phone screening where they will be asked non-sensitive questions (age, employment status, previous mindfulness training and willingness to be randomized and attend study visits and trainings) and told the eligibility criteria. If they are likely eligible and interested, they will be invited to continue with informed consent and screening for eligibility.

Eligible participants must: 1) be 21-65 years old (age limitations for both police departments); 2) demonstrate English fluency; 3) be a sworn LEO at the rank of Sergeant or below; 4) agree to random assignment to condition; and 5) be willing to complete assessments at multiple time points and participate in intervention groups. Individuals will be excluded from participation if they: 1) have participated in MBSR, MBRT or a similar mindfulness course, or 2) score in the severe range on brief screening measures of depression, suicidal ideation, alcohol use, or PTSD.

- Depression: Patient Health Questionnaire (PHQ-9; Score 20 or more = Severe)
- Suicidal Ideation: Concise Health Risk Tracking (CHRT; Agree or Strongly Agree on one or more “active suicidal ideation or plans” items #10, #11 and/or #12)
- Alcohol Use: Alcohol Use Disorders Identification Test (AUDIT; Score of 20 or more indicate high risk or almost certain dependence.)
- PTSD: The Primary Care PTSD Screen for *DSM-5* (PC-PTSD-5; Score of 5 or more)

Immediately following the screening, participants will be informed whether they are eligible for study participation. Those not meeting criteria or not interested will be offered a list of mental health and stress management community resources. Eligible and consenting individuals will make an individual appointment for a remote (via Zoom) baseline assessment.

We estimate screening will take approximately 20 minutes, based on experience with similar procedures. Research staff will enter de-identified screening data into a spreadsheet, which will be stored on a secure server.

### **6.2.2 Enrollment, Baseline, and/or Randomization**

#### **Enrollment**

Consent for study enrollment:

The study enrollment date is the day an individual who has met all the screening criteria signs (via REDCap) the informed consent form. A Randomization and Enrollment Form, documenting enrollment and allowable window between the enrollment date and randomization, will be entered into REDCap, a secure internet-based survey and data management software system housed on a secure server.

Randomization, immediately following completion of the baseline assessment procedure, must occur within 60 days of screening.

#### **Baseline Assessments**

- Adverse Childhood Events
  - Childhood Trauma Questionnaire
- Treatment Expectancy and Credibility
  - Expectancy/Credibility Questionnaire
- Proinflammatory Cytokines (C-RP, IL-6, IL-10, TNF- $\alpha$ )
  - Dried Blood Spot Collection Kit
- Psychological Resilience
  - Brief Resilience Scale
- Alcohol Misuse
  - PROMIS Alcohol Use
  - PROMIS Alcohol Use Negative Consequences
- Depression
  - PROMIS Depression
- Sleep Disturbance
  - PROMIS Sleep Disturbance
- Mindfulness
  - Five Facet Mindfulness Questionnaire – Short Form^138

- Self-Compassion
  - Self-Compassion Scale – Short Form^139
- Aggression
  - Buss Perry Aggression Questionnaire – Short Form^140
- Suicidal Ideation
  - Concise Health Risk Tracking - Self-Report
- Trauma Symptoms
  - PTSD Checklist for DSM5
- Burnout
  - Oldenburg Burnout Inventory
- Sustained Attention to Response Task
- Interoceptive Awareness
  - Multidimensional Assessment of Interoceptive Awareness-II
- Perceived Stress
  - Perceived Stress Scale-10^136

### **Randomization**

Immediately following completion of the Zoom-facilitated baseline assessment session, and confirmed completion of the dried blood spot sample, study staff not involved in data collection will randomly assign participants to condition using SPSS and REDCap. The study statistician will create an allocation table using SPSS, and upload it to REDCap, which will be used to implement the randomization procedure for all sites. All trial randomization codes will be stored within REDCap, which is a secure (HIPAA-compliant) internet-based survey and data management software system housed on a secure server at Oregon Health and Science University.

Participants will then be notified via phone of group assignment by a study team member. Participants assigned to MBRT and SME conditions will receive emailed information regarding course structure, dates/times, and class format. All participants will be provided information on assessment timeline, reminder calls they will receive, and contact information for the research team. Initiation of study intervention will be between 1 and 21 days. Participants assigned to SME or NIC will be offered an opportunity to participate in an MBRT course after the final 12-month follow-up collection of departmental excessive use of force data. Participants in all conditions will have access to resources provided by PPB, APD or MPD, including counseling services.

### **6.2.3 Blinding**

Throughout the study, all assessors will be blind to study condition. Interventionists and participants will not be blinded. No one will be authorized to break that blind, and at no point in

the study will assessors be unblinded.

#### **6.2.4 Followup Visits**

Postcourse followup (must occur within 21 days of end of 8-week intervention period).

- Proinflammatory Cytokines (C-RP, IL-6, IL-10, TNF- $\alpha$ )
  - Dried Blood Spot Collection Kit
- Psychological Resilience
  - Brief Resilience Scale
- Alcohol Misuse
  - PROMIS Alcohol Use
  - PROMIS Alcohol Use Negative Consequences
- Depression
  - PROMIS Depression
- Sleep Disturbance
  - PROMIS Sleep Disturbance
- Mindfulness
  - Five Facet Mindfulness Questionnaire – Short Form
- Self-Compassion
  - Self-Compassion Scale – Short Form
- Aggression
  - Buss Perry Aggression Questionnaire – Short Form
- Suicidal Ideation
  - Concise Health Risk Tracking - Self-Report
- Trauma Symptoms
  - PTSD Checklist for DSM-5
- Burnout
  - Oldenburg Burnout Inventory
- Sustained Attention to Response Task
- Interoceptive Awareness
  - Multidimensional Assessment of Interoceptive Awareness-II
- Perceived Stress
  - Perceived Stress Scale-10
- Global Impression of Change

- Acceptability
  - Acceptability of Assessment Procedures
  - Postcourse Satisfaction Survey (MBRT and SME)
- Intervention Compliance
  - Meditation Practice Questionnaire (MBRT)
  - Ilumivu (MBRT and SME)

3- and 6-month follow-up (must occur within  $\pm 10$  days of target date. Target date is relative to end of the intervention period, i.e., 90 days for 3-month followup, and 180 days for 6-month followup):

*Note: 6-month follow-up is final study visit.*

- Proinflammatory Cytokines (C-RP, IL-6, IL-10, TNF- $\alpha$ ) (**Only at 3-month follow-up**)
  - Dried Blood Spot Collection Kit
- Psychological Resilience
  - Brief Resilience Scale
- Alcohol Misuse
  - PROMIS Alcohol Use
  - PROMIS Alcohol Use Negative Consequences
- Depression
  - PROMIS Depression
- Sleep Disturbance
  - PROMIS Sleep Disturbance
- Mindfulness
  - Five Facet Mindfulness Questionnaire – Short Form
- Self-Compassion
  - Self-Compassion Scale – Short Form
- Aggression
  - Buss Perry Aggression Questionnaire – Short Form
- Suicidal Ideation
  - Concise Health Risk Tracking - Self-Report
- Trauma Symptoms
  - PTSD Checklist for DSM-5
- Burnout
  - Oldenburg Burnout Inventory

- Sustained Attention to Response Task
- Interoceptive Awareness
  - Multidimensional Assessment of Interoceptive Awareness-II
- Perceived Stress
  - Perceived Stress Scale-10
- Intervention Compliance
  - Meditation Practice Questionnaire (MBRT)
  - Ilumivu (MBRT and SME)

12-month Followup (must occur on target date, which is 360 days from the end of the intervention period):

- Excessive Use of Force (Individual-level LEO excessive use of force (i.e., aggressive drawing and discharge of weapons, vehicle rams, illegal takedowns, administrative and citizen complaints)
  - BlueTeam^96 Database and/or other departmental data

#### **6.2.5 Completion/Final Evaluation**

The final evaluation is the 6-month followup. See above for assessments.

Study coordinator will contact any participants who discontinue the intervention to identify reason for early termination (e.g., illness, not finding the intervention beneficial, schedule change). In the event a participant discontinues due to an intervention-related adverse event, study staff will continue to follow-up with the participant until the issue is resolved.

### **7. SAFETY ASSESSMENTS**

Minimal risks will exist for all participants involved in this project. Participants will be informed that MBRT and SME are considered to have very low risk for adverse events. These risks are considered to be minimal and are addressed in the consent forms.

In this study, the expected minimal risks to the subject are as follows:

- Minor **aches or strains** from mindful movement practices.
- Mild **emotional distress** completing self-report measures

To minimize risk during the mindful movement practices, participants will be instructed to recognize their physical limitations and to not exceed them. Given that this is an able-bodied population, and movement practices are very mild (e.g., gentle stretching) it is unlikely that injury will occur. To minimize risk related to completing the measures or procedures, participants will be notified during consent that participation is voluntary and that they can withdraw at any time.

## 7.1 Specification of Safety Parameters

At screening, individuals will be excluded from participation if they score in the severe range on brief screening measures of depression, suicidal ideation, alcohol use, or PTSD. Therefore, potential participants with severe mental illness and related safety issues will be excluded from the study and will be offered a list of mental health and stress management community resources.

## 7.2 Methods and Timing for Assessing, Recording, and Analyzing Safety Parameters

The interventions in this study are low risk. Therefore we do not anticipate intervention-related risk to participant safety. In addition to screening, suicidal ideation will also be assessed at baseline, post-intervention, 3- and 6-month follow-up. [name] (Portland and Madison) or [name] (Albuquerque) will contact any participant who endorses suicide risk as evidenced by Concise Health Risk Tracking (CHRT) endorsement of suicidal ideation (i.e., Agree or Strongly Agree on one or more “active suicidal ideation or plans” items #10, #11 and/or #12). Drs. [name] or [name] will gather more information and make an appropriate referral for mental health services.

## 7.3 Adverse Events and Serious Adverse Events

An **adverse event (AE)** is defined as any unfavorable and unintended diagnosis, symptom, sign (including an abnormal laboratory finding), syndrome or disease which either occurs during the study, having been absent at baseline, or if present at baseline, appears to worsen. Adverse events are to be recorded regardless of their relationship to the study intervention.

A **serious adverse event (SAE)** is defined as any untoward medical occurrence that results in death, is life threatening, requires inpatient hospitalization or prolongation of existing hospitalization, results in persistent or significant disability/incapacity, or is a congenital anomaly.

[name] (Portland and Madison) or [name] (Albuquerque) will contact any participant who endorses suicide risk as evidenced by Concise Health Risk Tracking (CHRT) endorsement of suicidal ideation (i.e., Agree or Strongly Agree on one or more “active suicidal ideation or plans” items #10, #11 and/or #12). Drs. [name] or [name] will gather more information and make an appropriate referral for mental health services.

Research staff will be trained to identify potential for risk and adverse events. All student research assistants will be advanced doctoral students in clinical psychology, both of the MPIs ([name] and [name]) and Co-I ([name]) are licensed clinical psychologists. Thus, the research team has an attunement to potential adverse events that will be augmented with training and preparation. Together, the training team will focus on preparing all team members to identify potential risks for adverse events and what steps to take if such risk occurs. Collection of AE's and SAE's will be unsolicited. If an AE or SAE occurs, trained study staff will adhere to the Report Procedures outlined in section 7.4.

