MBRT and SME groups will be led by separate interventionists, with at least masters level training in mental health or a related field, and matched for level of education and experience. MBRT interventionists will have previous training in and experience with MBRT or related interventions (e.g., MBSR, MBCT or MBRP), and will undergo intensive training, weekly clinical supervision, and regular meetings with MPIs to discuss fidelity and other clinical issues. Drs. [name], [name], and [name] are clinical psychologists with combined knowledge of psychoeducational protocols, MBIs, first responder populations, trauma, substance abuse, and other psychosocial outcomes. Given the importance of internal validity of interventions in RCT research, careful attention will be given to intervention adherence and consistency across sites, with all sessions being audio and video recorded. Under the supervision of [name], [name], and consultant [name], advanced graduate students at both study sites will review four randomly selected sessions from each MBRT cohort to assess intervention fidelity, adapting the MBRP Adherence and Competence measure used in previous trials. Drs. [name], [name], and [name], as well as consultant [name], will do the same for each SME cohort. Drs.

[name], [name] and [name] will provide weekly supervision to all interventionists to ensure fidelity and minimize drift. Participants in the NIC condition will not engage in a training; therefore, the administration of this group will only entail scheduling and meeting NIC participants for data collection.

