## 5. STUDY INTERVENTIONS

### 5.1 Interventions, Administration, and Duration

Both MBRT and SME will include psychoeducation, gentle movement exercises focused on stress reduction and fitness, and weekly homework assignments, and will be matched for time and assigned homework.

MBRT will be delivered in groups of 10 to 13 law enforcement officers, in 8 weekly sessions of 1 hour each, with the exception of weeks 1 and 7 which are extended 7- and 4-hour classes, respectively, for a total of 17 intervention hours. The extended session, modeled after MBSR, is intended to provide an immersive training experience. The session will contain a series of mindfulness practices, including body scan, mindful movement, and walking and breath-focused

meditations. The session will focus primarily on formal mindfulness practices, in contrast to inclusion of discussion and psychoeducational components contained in other MBRT sessions.

If state, local and university allow Sessions 1 and 7 to be in-person, they will be conducted at the study sites. If not, they will be conducted using the online Zoom platform. Any MBRT in-person intervention sessions will be held in reserved rooms able to accommodate up to 25 people, and large enough to comply with social distancing guidelines - specifically, the Psychology Research Lab in Portland, and at UNM Department of Psychology in Albuquerque. All MPD groups will be conducted remotely. Online groups will be facilitated via Zoom. MPI [name] and Co-Is [name] and [name] will oversee MBRT interventionist training. [name] co-developed MBRT, and is an expert in MBIs with first responders; [name] and [name] have facilitated, trained and supervised MBIs, and have collaborated on multiple MBI-related NIH trials.

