SME will be delivered as a weekly, 8-week, 1.5 hour class, except for weeks 1 and 7 which are extended to 4-hour classes, for a total of 17 intervention hours, with weekly homework (amount matched to MBRT), and gentle movement exercises. The content focuses on psychological, physiological, and dietary effects of stress, time management techniques, fitness, sleep hygiene, nutrition, and factors mitigating effects of stress. [name] (SME developer) will provide input and support to ensure interventionists are trained to fidelity. Training will be conducted by trainers approved by [name], with experience conducting SME and training interventionists. MPI [name], a licensed clinical psychologist with experience facilitating stress management groups, will oversee SME training with support from [name]. Potential adverse effects include: minor aches or strains from mindful movement practices, and mild emotional distress completing self-report measures or exposure to the socially evaluative cold pressor task challenge procedures.

MBRT and SME groups will be led by separate interventionists, with at least masters level training in mental health or a related field, and matched for level of education and experience. MBRT interventionists will have previous training in and experience with MBRT or related interventions (e.g., MBSR, MBCT or MBRP), and will undergo intensive training, weekly clinical supervision, and regular meetings with MPIs to discuss fidelity and other clinical issues. Drs. [name], [name], and [name] are clinical psychologists with combined knowledge of psychoeducational protocols, MBIs, first responder populations, trauma, substance abuse, and other psychosocial outcomes. They each have extensive experience developing, implementing, supervising, and assessing similar interventions.

Given the importance of internal validity of interventions in RCT research, careful attention will be given to intervention adherence and consistency across sites, with all sessions audio and video recorded. Under supervision of Drs. [name], [name], [name] and consultant [name], advanced graduate students at both study sites will review four randomly selected sessions from each MBRT and SME cohort, adapting the MBRP Adherence and Competence measure used in previous trials. Drs. [name], [name] and [name] will provide weekly supervision to all interventionists to ensure fidelity and minimize drift.

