Participants randomized to the NIC condition will not receive any intervention, but will participate in the same assessments as the two active intervention conditions (i.e., at baseline, post-intervention, 3- and 6-month follow-up). Assessment times will be yoked to those of the two active intervention conditions.

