The IMC will serve in accordance with the guidelines set forth in a charter provided to each member. IMC members will review and agree to the charter at the initial meeting. If changes to the charter are necessary, the IMC will review and affirm their agreement with the changes. Their concurrence will be noted in the IMC meeting summary. The IMC will typically meet twice a year, or as deemed necessary. A quorum of more than half of the IMC members is required to convene a meeting of the IMC. The IMC will approve the final protocol of the study before the study begins enrolling participants. In monitoring the data and safety throughout the trial, the IMC may recommend continuation of the trial, modifications to the trial, or termination of the trial in the event of overwhelmingly significant efficacy difference between groups or unacceptable adverse events.

Study progress and safety will be reviewed monthly (and more frequently if needed). Progress reports, including participant recruitment, retention/attrition, and AEs will be provided to the IMC members following each of the quarterly reviews. An Annual Report will be compiled and will include a list and summary of AEs. In addition, the Annual Report will address: (1) whether AE rates are consistent with pre-study assumptions; (2) reason for dropouts from the study; (3) whether all participants met entry criteria; (4) whether continuation of the study is justified on the basis that additional data are needed to accomplish the stated aims of the study; and (5) conditions whereby the study might be terminated prematurely. The Annual Report will be sent to the IMC and will be forwarded to the IRB and NCCIH. The IRB and other applicable recipients will review progress of this study on an annual basis.

The study team will generate annual Study Reports for the IMC and will provide information on the following study parameters: recruitment, retention, enrollment by month, demographics, subject status, treatment duration, and AE status. Study Report tables will be generated only from aggregate (not by group assignment) baseline and aggregate safety data for the study population. A separate Closed Safety Report, with unmasked group baseline and safety data, will be generated for the IMC by a designated unmasked member of the team, but

will not be reviewed by the study team. As noted above, we will also review quarterly with the IMC subject accrual, subject status, adherence data, AEs and SAEs.

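### Adverse events are recorded only when volunteered, so MBRT or SME counts are not comparable with NIC, mainly during the 8-week course

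*Combined protocol and SAP*

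**What the plan says.** Section 7.3 defines an adverse event broadly, as any new or worsened diagnosis, symptom or sign, and adds: "Adverse events are to be recorded regardless of their relationship to the study intervention". NIC events therefore count in the same way as MBRT events. The same section then says: "Collection of AE's and SAE's will be unsolicited". The schedule in Section 6.1 has no adverse event row, and the visit lists in Sections 6.2.2 and 6.2.4 contain no adverse event item. The one safety measure that is asked about is suicidal ideation, by the CHRT at every assessment, with no restriction by arm (Section 7.2).

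On contact with staff, Section 5.2 says of MBRT and SME: "They will both be delivered in 8 weekly sessions with a total training time of 17 hours". For NIC, Section 3 says that "the administration of this group will only entail scheduling and meeting NIC participants for data collection". Section 5.1 adds that NIC officers "will participate in the same assessments as the two active intervention conditions". All participants are invited to one feedback phone interview (Précis, Sample Size and Population).

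Section 9.2 provides for asking dropouts why they left. It includes whether the officer had an adverse event due to the intervention, but only for officers in MBRT or SME.

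Under Section 9.4 the committee receives "A separate Closed Safety Report, with unmasked group baseline and safety data". It may recommend termination for unacceptable adverse events. One stopping criterion is that the intervention is associated with adverse effects that put its safety in doubt.

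**The concern.** The scope (every event, related or not, in all arms) and the method (wait for the officer to mention it) do not fit together when the arms differ in how often officers meet staff. An officer with a strained back in week 3 of MBRT sees trained staff that week and the next. An NIC officer with the same strain has no scheduled staff contact until the post-intervention assessment.

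Two further provisions lean the same way. The withdrawal inquiry about adverse events leaves out NIC. In the feedback interview, the sample questions on the training and on changes noticed go only to MBRT and SME, while those for all groups concern trial conduct and assessment burden (Section 9.6).

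At stake is how the Closed Safety Report is read. An excess over NIC could come from contact alone, and a real excess could not be told apart from it. This is also the trial in which procedures for a later efficacy trial are to be settled, so the collection method may carry forward.

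**Working it through.** **Step 1: the plan's own contact figure.** MBRT: six 1-hour sessions plus "with the exception of weeks 1 and 7 which are extended 7- and 4-hour classes, respectively, for a total of 17 intervention hours", so 6 × 1 + 7 + 4 = 17 hours. SME: six 1.5-hour sessions, "except for weeks 1 and 7 which are extended to 4-hour classes, for a total of 17 intervention hours", so 6 × 1.5 + 2 × 4 = 17 hours. Both reproduce. The active arms match at 8 sessions and 17 hours.

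**Step 2: scheduled contacts after randomization.** Active arms: 8 sessions + 3 assessments + 1 interview = 12. NIC: 3 + 1 = 4. Without the interview the counts are 11 and 3. Within the 8 weeks, sessions are 8 versus 0. Reminder calls go to all arms and are not counted.

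**Step 3: why contact counts alone overstate the effect.** If every event could surface at every contact, the recorded share would be 1 − (1 − p)^k, where k is the number of contacts and p is an assumed chance of reporting at each. For 12 versus 4 the ratio is 0.460/0.185 = 2.48 at p = 0.05 and 0.718/0.344 = 2.09 at p = 0.10. This holds only for events before session 1. An event in week 6 cannot be reported at sessions 1 to 5, and an event after session 8 has the same scheduled contacts in every arm.

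**Step 4: allowing for timing.** Assumptions: equal true rates; events uniform over 34 weeks; sessions mid-week in weeks 1 to 8; post-intervention assessment at week 9; interview at week 9.5; follow-ups at weeks 21 and 34 (8 + 90/7 = 20.9 and 8 + 180/7 = 33.7, from the targets in Section 6.2.4); contacts independent and equally likely to elicit a report.

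For an event in the course, the number of sessions still to come, J, is 8 or 0 with weight 1/16 each, and 1 to 7 with weight 2/16 each. The mean of (1 − p)^J is 0.8204 at p = 0.05 and 0.6763 at p = 0.10. With m later contacts, the recorded share is 1 − (1 − p)^m × that mean in the active arms and 1 − (1 − p)^m in NIC.

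- m = 3 (no interview): p = 0.05 gives 0.297/0.143 = 2.08; p = 0.10 gives 0.507/0.271 = 1.87.
- m = 4 (interview): p = 0.05 gives 0.332/0.185 = 1.79; p = 0.10 gives 0.556/0.344 = 1.62.

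Over the whole study, weight each share by the weeks it covers. Without the interview at p = 0.05, NIC is (9 × 0.1426 + 12 × 0.0975 + 13 × 0.05)/34 = 0.091. The active arms add 8 × (0.2966 − 0.1426)/34, giving 0.128 and a ratio of 1.40. The other cells follow in the same way.

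| Assumed p | Study, no interview | Study, interview | Course, no interview | Course, interview |
|---|---|---|---|---|
| 0.05 | 1.40 | 1.33 | 2.08 | 1.79 |
| 0.10 | 1.31 | 1.25 | 1.87 | 1.62 |
| 0.30 | 1.1 | 1.1 | 1.35 | 1.21 |

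Events after week 8 have a ratio of 1.0 throughout. MBRT versus SME has a ratio of 1.0 throughout.

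**The case against.** The best case for the plan is that this is a feasibility trial with low expected risk (Section 7 lists minor aches and mild distress), no safety hypothesis and no formal by-arm test of adverse events. The by-arm data go to an independent committee that includes a biostatistician, and events are classified by severity and relatedness (Section 7.4), so raw counts are not all it sees. PTSD symptoms, depression, alcohol misuse, sleep disturbance, medication use and psychological treatment are collected in all arms at every assessment, which would show psychological worsening symmetrically. Staff are trained to recognise adverse events.

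Much of this stands, and it limits the consequence. It does not remove the problem. No rule turns a worse score or a new treatment into an adverse event. The scales do not cover strains, injuries or hospital stays. Staff training helps only where there is contact. A descriptive table can mislead without a test.

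An opposite pull is also possible. Officers are asked not to reveal their arm to data collectors (Section 9.2.1), which could suppress intervention-related reports at assessments. That is a further ascertainment weakness.

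A reader might infer from the contact counts that active-arm events would be recorded two to three times as often as NIC events, or that every by-arm safety comparison is biased. The documents support neither. The first ignores that most of the follow-up falls after the sessions end, when contacts are equal. The second overlooks the matched MBRT and SME schedules and the CHRT, which is asked in all arms.

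**Conclusion.** The point holds for MBRT versus NIC and SME versus NIC, mainly for events during the 8-week course. It does not touch MBRT versus SME or suicidal ideation measured by the CHRT. The unequal opportunity to report follows directly from the text. Its numerical size does not, because the documents give neither a reporting probability nor an event rate.

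Under the stated assumptions with p of 5% to 10%, the active/NIC ratio of recorded events is about 1.25 to 1.40 over the study and 1.6 to 2.1 within the course. It moves toward 1 as p rises. The expected direction is over-recording in the active arms relative to NIC, subject to the possible offset from the masking request.

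This is a cheap improvement worth making. It does not threaten the trial's main aims.

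**What to change.** Add one identical item to the existing post-intervention, 3-month and 6-month online surveys in all three arms: any new or worsened symptom, injury or hospital stay since the last assessment. Add the matching row to the schedule in Section 6.1 and amend Section 7.3. Base the by-arm table in the Closed Safety Report on these solicited events and list volunteered events separately. At withdrawal, ask about adverse events in all three arms.

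Scheduled opportunities for the by-arm table are then 3 versus 3. Officers still know their arm, so reporting habits may differ, but the opportunity no longer does.

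Keeping the two sources apart matters. If volunteered session reports were pooled with the solicited ones, the ratio for an event preceding all contacts would be [1 − (1 − q)^8 (1 − s)^3] / [1 − (1 − s)^3]. With an assumed item sensitivity s = 0.5, this is 0.917/0.875 = 1.05 at q = 0.05 and 0.979/0.875 = 1.12 at q = 0.20.

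The cost is one survey item at three existing time points, one question at withdrawal and some extra minor adverse event forms. No visit or staff is added.
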